While IV Cytoxan (CYC) administration per NIH protocol was the standard of care for the treatment of renal disease in SLE, the serious side effects led to a continued search for new approaches. Studies have shown that Mycophenolate Mofetil (MMF) provides comparable efficacy to IV CYC for both induction and maintenance with fewer side effects [13-17, 20]. MMF is an immunosuppressive agent that suppresses *de novo* purine synthesis by selectively inhibiting inosine-5'-monophosphate dehydrogenase. Unlike other cell types, lymphocytes are heavily dependent upon this mechanism for proliferation. As a result, MMF is capable of decreasing the proliferation of lymphocytes and the production of autoantibodies without the cytotoxic or mutagenic effects of CYC [18, 19]. Clinical trials comparing these two medications are discordant in their response rates but uniformly show them to be equivalent in efficacy. In the study conducted by Chan *et al.*, 95% of patients achieved clinical response (both complete and partial) with MMF (32 patients) and 90% with CYC (30 patients) [14]. In contrast, in the study by Ginzler *et al.*, only 52% responded to MMF (71 patients) and 30% to CYC (69 patients) [16]. The disparity observed between the Chan and Ginzler studies may be attributed to inherent differences in design and patient population. However, 90% response rates have never been reported in any of the LN studies. ASPREVA, in their clinical trial results, showed a 56% response rate with MMF and 53% with CYC. Each of the 370 LN patients was randomized to either a target MMF dose of 3 g/day or an IV CYC dose of 0.5 to 1 g/m² monthly for a 24 week induction period. The primary outcome was a specified decrease in urine protein-creatinine ratio and stabilization or improvement of serum creatinine [20]. The current standard of care treatment for SLE patients with Class III and Class IV glomerulonephritis consists of high doses of corticosteroids, accompanied by MMF. A summary of all these clinical trials is presented in Table 1.

For the current study background, induction therapy is suggested to be MMF with a target dose of 3g/day for 6 months. Based on the data from the published clinical trials summarized in Table 1, the expected complete response rate is predicted to be 20%. Clinical response (both complete and partial) is expected to be 50%.

Rationale for ACTH

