Recurrent renal flares cause renal damage leading to glomerulosclerosis and irreversible deterioration of renal function [9]. Safe and effective maintenance therapies are needed to prevent renal relapses, reduce progression to ESRD, and reduce the chance of adverse events. Clinical trials focusing on maintenance therapies by Contreras *et al.* [13], ALMS (Aspreva Lupus Management Study) [26] and Houssiau *et al.* (MAINTAIN) [27] suggest that MMF is at least equivalent to AZA for maintenance therapy. A summary of the maintenance trials is presented in **Table 3**. The current study patients will be maintained on MMF for total treatment duration of 2 years.

Non-immunomodulatory treatments are also used in the treatment of LN patients. These include ACE inhibitors, ARBs, and statins and are not restricted in this study.

C. RESEARCH DESIGN AND METHODS

Study Design

The study is a randomized, controlled phase IV, single center trial of ACTHar plus CellCept (Mycophenolate Mofetil), as defined by the ASPREVA Nephritis Trial (MMF 3000 mg daily) in the treatment of lupus nephritis. The primary outcome will be assessed at 6 months. Thereafter, subsequent therapy will be with CellCept maintenance 2000 mg daily.

Study Duration

Follow-ups for each patient will be conducted for a total of 24 months.

Primary Outcome

The proportion of participants who achieve a complete response at 6 months.

1. Complete response (CR) is defined as *all* of the following criteria having been achieved:
 - a. Stabilization of estimated glomerular filtration rate (i.e., a 6-month eGFR level \pm 10% of baseline) or improvement if the screening value is changed from patient's baseline
 - b. Inactive urinary sediment (red blood cells per high-power field [RBCs/HPF] <5-10, not due to gyn bleeding)
 - c. Urine protein/creatinine ratio <0.5

Secondary Outcomes

1. Frequency of responders = CR + Partial Responders (PR). PR = improvement from baseline of at least \geq 50% in all abnormal renal parameters (proteinuria and serum creatinine) without deterioration of any measurements at 6 months
2. Frequency of extra-renal flares as defined by the SELENA-SLEDAI Flare Index. Extra-renal disease activity measured by SELENA-SLEDAI and BILAG
3. Steroid -like side effects: increased in BP by 20 mmHg for both SBP and DBP, increased blood sugar with a fasting plasma glucose level \geq 126 mg/dl, weight gain \geq 10% of the initial weight, infections
4. Side effects

Inclusion Criteria

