Dose finding study of patients with a recent flare of LN, and biopsy proven LN (Class III, IV) treated with CellCept 3 grams daily and ACTHar gel 80 U biw or Acthar gel 80 U qod. The dose of 80 U biw was chosen based on the published literature in MN. However, in an attempt to improve outcomes we also suggest a higher dose of 80 U qod to be used for one month of "induction". Patients in the 80 U qod arm will be tapered to 80 biw after the first month of therapy. In all groups, patients can be on a prednisone dose of ≤ 20 mg prior to initiating therapy with CellCept or ACTHar. Based on the investigator's judgment, patients will be switched to oral prednisone for worsening lupus nephritis or extra-renal lupus. Patients will be maintained on ACTHar for a total of 3 months. Patients with partial response will be offered the option to continue ACTHar 80 U biw for a total of 6 months. Each dosing arm will include 10 patients.

Biomarkers

Patients whose renal biopsies are available (we expect that 80% of patients will have a biopsy done within 1 month of the screening visit) will have frozen sections stained for MCR using anti-MCR antibodies in the manner described by Gong [35]. Similarly, skin biopsy samples obtained at D 0 and week 24 will be stained for MCR. The readout of MCR activation by ACTH in the skin will be ICAM-1, VCAM1, mEPCR. Also, levels of ICAM-1, VCAM-1, and E-selectin will be evaluated in urine samples collected at D 0, weeks 4, 12 and 24. Our center has extensive expertise in the measurement of these cytokines. Our collaborator [name] will supervise the work of examining all biomarkers. We hypothesize that dermal and urinary biomarkers are likely to decrease faster in response to treatment with ACTHar as a consequence of the direct activation of the MCR.

Treatment Overview

Screening protocol –as per attached schedule of assessments

CONCOMITANT MEDICATIONS

Participants may receive all required and non-prohibited concomitant medications as clinically indicated. Prednisone in a dose of ≤ 20 mg daily is allowed at study entry, but should be tapered to below 10 mg daily as tolerated by week 24.

Prophylactic Medications

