The investigator will maintain adequate records of the disposition of the investigational agent, including the date and quantity of drug that was received, the participants to whom the drug was dispensed (participant by participant accounting), and an account of any drug accidentally or deliberately destroyed. Records for receipt, storage, use, and disposition of the study drug will be maintained on site. A drug-dispensing log will be kept current for each participant and will contain the identification of each participant and the date and quantity of drug dispensed. All records regarding disposition of the investigational product will be available for inspection by Questcor.

ASSESSMENT OF COMPLIANCE WITH STUDY MEDICATION

ACTH and MMF compliance will be checked at each visit.

Dosage and Administration of Acthar *Daily /weekly dose, administration, frequency*

Patients will be treated with CellCept 3 grams daily and randomly assigned to ACTHar gel 80 U biw or Acthar gel 80 U qod.

The dose of 80 U biw was chosen based on the published literature in MN [30].

In an attempt to improve outcomes, we also suggest a higher dose of 80 U qod to be used for one month of “induction”. Patients in the 80 U qod will be tapered to 80 biw after the first month of therapy.

Patients will be maintained on ACTHar for a total of 3 months.

Patients that do not achieve complete response at week 12 will be offered the option to continue ACTHar 80 U biw for a total of 6 months, or 24 weeks.

Laboratory Testing and Study Schedule --see schedule of events

Patient Monitoring and Evaluation *Contingencies for patients not responding (i.e. dose adjustment, schedule change)*

Glucocorticoids may be increased during the study for worsening renal and extra-renal manifestations of SLE. The dose may be increased as required by the clinical manifestations up to 1 mg/kg/d. ACTHar will be discontinued and patients will be considered non-responders. Renal relapses, as defined by increase in proteinuria at two consecutive visits will require discontinuation of the study regimen and treatment based on investigator preference.

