The major short-term side-effects of ACTH are salt and water retention, hypertension, hyperglycemia, central nervous system stimulation, peptic ulceration and immunosuppression. While such effects are reversible, if the use is prolonged, additional adverse effects including osteoporosis, cataracts, skin fragility, myopathy, Cushingoid facies, hirsutism, alopecia, fat re-distribution, and striae may occur, as well as infections which can be life-threatening.

Potential Pitfalls and Contingencies *Describe plans to address possible problems*

Study Drug Discontinuation

1. SLE Extra-renal Flare—severe BILAG A or SLEDAI flares
2. Renal Flare – increase proteinuria by 30% and/or increased in creatinine by 25% over the baseline visit 0, confirmed by repeat analysis. Proteinuria needs to be confirmed by a 24 hour urine P/C ratio.
3. ACTHar related steroid-like side effects – HTN, DM, hypoK refractory to optimal management
4. Severe life-threatening infections

Study drug can be decreased for ACTHar related AE, as described above. Patients will be closely monitored to document maintained efficacy. We propose the following taper regimen, 80 mg qod, decreased to 80 mg biw for one week if AE continues, decrease to 60 biw for one week, then 40 biw, and finally 20 biw.

If the study drug is discontinued for SLE related increased activity, the patients will be treated with the appropriate dose of prednisone and continued to be followed up until resolution of the symptoms. At the end of the 3 month treatment period, ACTH will be discontinued. In the event of adrenal insufficiency upon discontinuing the drug either for side effects or end of therapy, the previous dose of ACTH will be restarted and the above taper regimen will be followed.

Data Processing and Analysis

Statistical /Analytical Plan *Include data management and quality assurance*

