Clinical response data will be evaluated every 3 months and reported as overall percent responders and complete and partial responders in each dosing arm. Also, side effects (including steroid-like side effects) will be evaluated every 3 months and reported to the IRB and Questcor. The observed response rates in this study will be compared to the historical expected complete response rate in LN of 20%, and total renal responses of 50%. A two-sided chi-square test will be used to compare the proportion of subjects with complete response and total responses between the treatment arms and these expected values. Differences in the baseline characteristic between the two treatment groups will be evaluated using descriptive statistics, the two-sample t-test for continuous variables and the chi-square test for categorical variables. Times to event for the endpoints of partial and complete remission will be analyzed with the use of the Cox proportional-hazards model. The proportion of SAEs in the study regimen will be compared with the expected SAEs from other lupus nephritis studies using a two-sided chi-square test at the 0.05 level of significance without using continuity correction.

The research will be conducted as per CUMC's strict guidelines, thus preventing unauthorized collection, use, and/or disclosure of data. Strict physical, technical, and administrative safeguards to protect data from unauthorized access and/or tampering will be in place. Appropriate measures to ensure confidentiality will be employed. The aggregate data will be entered in a database. The data will be kept in locked facilities that can only be accessed by study investigators or a member of the research team. This will be for a period of up to 10 years, after which the data collection forms and database from this study will be destroyed.

Sample Size Justification *Include power analyses or justification for enrollment plan*

N=10 patients per dosing arm.

References

2. Lam G, Petri, M: Assessment of systemic lupus erythematosus. *Clin Exp Rheumatol* 2005, 23:S120-S132.

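### Complete response cannot be scored one way as written: the eGFR criterion literally fails a rise above 10%, its reference value is unclear, and the red-cell limit is a range

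*Combined protocol and SAP*

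**What the plan says.** Under Primary Outcome (section C), complete response (CR) requires all of three criteria.

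- **1a, eGFR.** Stabilization is spelled out as a 6-month eGFR within plus or minus "10% of baseline) or improvement if the screening value is changed from" the patient's baseline. Improvement therefore counts only where the screening value differs from that baseline.
- **1b, sediment.** "Inactive urinary sediment (red blood cells per high-power field [RBCs/HPF] <5-10, not due to gyn bleeding".
- **1c, proteinuria.** A urine protein/creatinine ratio below 0.5, which is a single cut-off.

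Three other places bear on how CR is read and used:

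- The rationale for MMF describes the outcome of the cited 370-patient trial as including "stabilization or improvement of serum creatinine", with no upper limit mentioned.
- Study Drug Discontinuation ties its renal-flare rule to a named visit: "increased in creatinine by 25% over the baseline visit 0, confirmed by repeat analysis". That definition is not carried over to 1a.
- The Statistical/Analytical Plan says: "Clinical response data will be evaluated every 3 months and reported as overall percent responders and complete and partial responders in each dosing arm". It compares CR with the "historical expected complete response rate in LN of 20%, and total renal responses of 50" percent, and does not restate or clarify the CR criteria.

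**The concern.** Because all criteria must hold, 1a or 1b alone can turn a responder into a non-responder.

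Two of the three criteria do not give one answer for every patient. The band in 1a has an upper edge, and the only way past it is closed to a patient whose screening value is unchanged. For a patient whose screening value has changed, the text does not say which value is the reference, how large the gain must be, or how large a difference makes the value changed. This may not be rare, since Treatment Description speaks of patients with a recent flare. In 1b a range stands where a limit should be.

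At stake is the integrity of the primary endpoint. Treatment is open-label and responders are tabulated by arm every 3 months. Whoever settles the red-cell cut-off or the meaning of baseline may do so knowing which choice favours which result. With 10 patients per arm, a single such decision is visible in the result.

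**Working it through.** The plan gives no figure to reproduce: the sample-size section states 10 per arm with no derivation. The check is therefore to apply the criteria to illustrative values, and then to measure what one reclassified patient does to the planned test. The eGFR values are illustrations, not trial data.

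**1a, unchanged screening value of 80.** The band is 0.9 × 80 = 72 to 1.1 × 80 = 88. A 6-month value of 72 (a 10% fall) passes. A value of 90 is 90/80 = +12.5%; it lies outside the band and the improvement route is closed, so it fails.

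**1a, changed screening value: pre-flare 90, screening 60.** The band is 0.9 × 60 = 54 to 1.1 × 60 = 66 if baseline is the on-study value, and 0.9 × 90 = 81 to 1.1 × 90 = 99 if it is the pre-flare value.

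| 6-month eGFR | Band around 60 | Band around 90 | Improved from 60 | Improved from 90 |
|---|---|---|---|---|
| 60 | pass | fail | no | no |
| 75 | fail | fail | yes | no |

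The patient at 60 passes or fails according to which value is baseline. The patient at 75 is outside both bands, so the result depends only on what improvement is measured from.

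**1b.** A count of 5 to 9 red cells per field is inactive under <10 and active under <5.

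**Effect of one patient.** Inputs are n = 10 per arm and the historical CR rate of 20%, both from the plan. The plan states the 0.05 level and the absence of continuity correction only for the comparison of serious adverse events. Using either for CR is an assumption, as is testing each arm separately. The one-sample statistic is (x − 10 × 0.2)² / (10 × 0.2 × 0.8) = (x − 2)² / 1.6. With correction, |x − 2| is reduced by 0.5 before squaring.

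| CR count | Uncorrected | p | Corrected | p | Exact binomial p |
|---|---|---|---|---|---|
| 4/10 | 4/1.6 = 2.50 | 0.114 | 2.25/1.6 = 1.41 | 0.236 | 0.121 |
| 5/10 | 9/1.6 = 5.63 | 0.018 | 6.25/1.6 = 3.91 | 0.048 | 0.033 |

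One patient shifts the arm by 1/10 = 10 points, and the step from 4 to 5 crosses 0.05 under all three tests. Away from that step it does not: 2/10 to 3/10 moves the uncorrected p from 1.00 to 0.43.

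If the arms were pooled (n = 20, statistic (x − 4)²/3.2), the uncorrected step lies between 7/20 (p=0.094) and 8/20 (p=0.025). With correction, 8/20 gives p=0.0504, so the step moves to 9/20 (p=0.012).

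**The case against.** The strongest reply is that the upper edge of the band should not be taken literally. The criterion is about stabilization, and the MMF rationale describes its model trial in terms of stabilization or improvement. A reader might infer that the plan means to fail patients whose kidney function improves. The documents do not support that, and a wording correction is enough. Intent does not, however, settle which baseline applies or which red-cell limit is meant.

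A reader might also infer that, with no minimum gain, trivial improvements will count as CR. This is largely moot if baseline is the on-study value: 50 to 51 already lies inside 0.9 × 50 = 45 to 1.1 × 50 = 55. The missing minimum matters only if the band is centred on a pre-flare value. Measuring improvement from screening is also the natural reading, although it is not stated.

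Nor can one say that the whole plan leaves baseline undefined. The schedule of assessments is attached to the protocol but not supplied, and it might name the visit. That alone would not remove the upper edge of 1a or make 1b a single number.

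A further temptation is to quote a chance that the conclusion changes. It depends almost entirely on the share of patients who are CR only under the lenient reading, and the documents give none. Take a strict CR rate of 20% and per-arm testing. Assumed shares of 1% to 2% give about 0.7% to 1.5%; shares of 5%, 10% and 20% give 5%, 12% and 33%. That range mostly returns the assumption, and part of the fragility comes from having 10 patients per arm whatever the wording.

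Finally, the open-label reporting shows an opportunity to choose a definition with results in view. It is not evidence that anyone has done so or will.

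**Conclusion.** The concern holds in this form and should be fixed. As written, 1a gives a wrong classification for an unchanged screening value (72 passes and 90 fails, from 80). It gives no single classification for a changed one, and 1b does not state one cut-off. Nothing in the supplied text repairs any of these.

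The firm part of the size is that one reclassified patient is 10 percentage points in an arm, and can carry the comparison with 20% across 0.05 at 4/10 versus 5/10. This rests on an assumed alpha of 0.05 and per-arm testing; it does not depend on the continuity correction. How many patients are affected is unknown, so no expected bias or error rate can be given.

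**What to change.** Amend the CR definition before outcomes are classified:

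- **(a)** Make the stabilization limit in 1a one-sided: 6-month eGFR at least 90% of the value at one named baseline visit, with no upper limit.
- **(b)** If the improvement route is kept for patients who enter below their usual eGFR, state once the value it is measured from, its minimum size, and what counts as changed. If (a) names an on-study visit, anyone who improves from it already passes. The amendment should then say whether this route is meant to require recovery.
- **(c)** Fix one red-cell cut-off for the primary analysis and report the other as a sensitivity analysis.

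The cost is a short amendment; no new data are needed. The CR rate may move slightly: up when the upper edge goes, or down with the stricter red-cell limit or a recovery requirement. Some comparability with the historical 20% may be lost.

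Separately, the offer to extend ACTHar is worded in two ways. Treatment Description has "Patients with partial response will be offered the option to continue ACTHar", while Dosage and Administration of Acthar has "Patients that do not achieve complete response at week 12 will be offered the option to continue". These must be reconciled. The point does not bear directly on the 6-month endpoint.

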1. Diagnosis of systemic lupus erythematosus (SLE) by American College of Rheumatology (ACR)/SLICC criteria
2. Age \geq 16 years
3. Active lupus nephritis defined by:
 - a. Kidney biopsy documentation of International Society of Nephrology/Renal Pathology Society (ISN/RPS) Class III or Class IV proliferative nephritis (including Class V occurring in combination with Class III or IV) within 12 months, and a urine protein/creatinine ratio >1 at time of entry to study
4. Ability to provide informed consent

Exclusion Criteria

1. Moderately severe anemia (Hgb < 8 mg/dL)
2. Neutropenia ($< 1,000/\text{mm}^3$)
3. Thrombocytopenia (platelets $< 50,000/\text{mm}^3$)
4. Positive purified protein derivative (PPD) test confirmed by positive Quantiferon TB gold.
5. Pulmonary fibrotic changes on chest radiograph consistent with prior healed tuberculosis
6. Active infections that in the opinion of the investigator increase the risks to the subject.
7. Known human immunodeficiency virus (HIV) and hepatitis B or C
8. End-stage renal disease (estimated GFR clearance $< 20 \text{ mL/min}/1.73 \text{ m}^2$)
9. History of cancer, except carcinoma in situ and treated basal and squamous cell carcinomas
10. Pregnancy
11. Lactation
12. Unwillingness to use a medically acceptable form of birth control (including but not limited to a diaphragm, an intrauterine device, progesterone implants or injections, oral contraceptives, the double-barrier method, or a condom)
13. Previous failure to respond to MMF
14. Use of rituximab within the past year
15. Use of experimental therapeutic agents within the past 60 days
16. Greater than or equal to 5 times the upper limit of normal of liver function tests (aspartate aminotransferase [AST], alanine aminotransferase [ALT], or alkaline phosphatase)
17. Severe, progressive, or uncontrolled renal, hepatic, hematological, gastrointestinal, pulmonary, cardiac, or neurological disease (or, in the investigator's opinion, any other concomitant medical condition that places the participant at risk by participating in this study) with the exception of diseases or conditions related to active SLE
18. Current substance abuse

Treatment Description

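### Read literally, partial response sets a harder kidney-function test than complete response, so total response against the fixed 50% can depend on how partial response is read

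*Combined protocol and SAP*

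**What the plan says.** All references are to the combined protocol and SAP.

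- **CR, kidney function** (section C, Primary Outcome, item 1a): "Stabilization of estimated glomerular filtration rate (i.e., a 6-month eGFR level" within 10% of baseline, "or improvement if the screening value is changed from" the patient's baseline. No size of improvement is given. CR also needs inactive sediment and UPCR below 0.5.
- **PR** (Secondary Outcomes, item 1): at least 50% improvement from baseline "in all abnormal renal parameters (proteinuria and serum creatinine) without deterioration of any measurements at 6 months". Responders are CR plus PR.
- **Who can enter:** Inclusion Criterion 3a requires active nephritis on biopsy "and a urine protein/creatinine ratio >1 at time of entry to study". Exclusion Criterion 8, "End-stage renal disease (estimated GFR clearance" below 20), is the only numeric renal limit, so a raised creatinine is permitted. Treatment Description calls the trial a "Dose finding study of patients with a recent flare of LN".
- **Analysis** (Statistical/Analytical Plan): response rates are compared with a "historical expected complete response rate in LN of 20%, and total renal responses of 50" per cent by two-sided chi-square, and Cox models are planned for time to partial and to complete remission. Both arms receive ACTHar, 10 patients each.
- **Worsening elsewhere** (Study Drug Discontinuation, item 2): a renal flare is "increase proteinuria by 30% and/or increased in creatinine by 25% over the baseline visit 0". PR gives no such threshold.

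**The concern.** A lower response level should include everyone who meets the higher one. Here CR is satisfied by a raised creatinine that stays put, while PR asks for that creatinine to improve by half. Two patients with identical kidney function and UPCR of 0.4 and 0.6 can therefore be a CR and a non-responder, with no step between.

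This matters because total response is judged against a constant, without an arm free of ACTHar. A rate set against a historical figure depends directly on how response is defined. The one comparator definition that the protocol describes, from the 370-patient MMF-versus-cyclophosphamide trial (Rationale for choosing MMF as background therapy), accepted a stable serum creatinine. The Cox analysis is also touched: a patient can reach complete remission without ever having met the partial rule.

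**Working it through.** The sample size section gives 10 per arm without power or effect size, so there is no planned figure to reproduce. The check applies both rules to example patients and then asks what one reclassified patient does to the planned test.

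**Assumptions.** Example patients are illustrative, have inactive sediment and meet the eGFR entry limit. The upper limit of normal creatinine (ULN) is taken as 0.9 to 1.2 mg/dL. The test is taken as a one-sample, two-sided chi-square of each arm against 50%, at 0.05 without continuity correction (the plan states these last two only for the SAE comparison).

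**Step 1: proteinuria is nested from the entry value.** Entry UPCR is above 1 and CR needs below 0.5, so every CR is a fall of more than (1 − 0.5)/1 = 50%.

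**Step 2: kidney function is not.**

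- *Chronically raised, stable.* Creatinine is 2.0 at both visits, the patient's usual level. The eGFR part of CR is met. UPCR 4.0 to 0.4 is CR. UPCR 4.0 to 0.6 is a fall of (4.0 − 0.6)/4.0 = 85% but not CR. For PR, 50% of the absolute value needs creatinine 2.0 × 0.5 = 1.0. Half of the excess over normal needs 2.0 − (2.0 − ULN)/2 = 1.45, 1.50 or 1.60 for ULN 0.9, 1.0 or 1.2. A value of 2.0 fails each: non-responder.
- *Recent flare, modest improvement.* Creatinine goes from 2.0 to 1.7. This is improvement under the second limb of CR item 1a. For PR it is 0.3/2.0 = 15% of the absolute value, or 0.3/1.1 = 27%, 0.3/1.0 = 30%, 0.3/0.8 = 37.5% of the excess over normal. With UPCR 0.6: non-responder.
- *Normal creatinine.* eGFR goes from 90 to 84, a fall of 6/90 = 6.7%. CR tolerates it. PR allows no deterioration, so with zero tolerance the patient fails PR.

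**Step 3: effect of one patient.** Chi-square = (x − n/2)²/(n/4).

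| Responders | Chi-square | p | Exact 95% CI |
|---|---|---|---|
| 8/10 | 3.60 | 0.058 | 44.4–97.5% |
| 9/10 | 6.40 | 0.011 | 55.5–99.7% |
| 2/10 | 3.60 | 0.058 | 2.5–55.6% |
| 1/10 | 6.40 | 0.011 | 0.3–44.5% |
| 14/20 (pooled) | 3.20 | 0.074 | 45.7–88.1% |
| 15/20 (pooled) | 5.00 | 0.025 | 50.9–91.3% |

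**Step 4: how often the two rules would disagree.** Let pN be total response under a nested rule, and d the share of all patients who respond under it but not under the present rule. Discordance is assumed to run in that direction only. In an arm of 10, the counts responding under both, nested only and neither are trinomial with probabilities pN − d, d and 1 − pN. The chance of at least one discordant patient is 1 − (1 − d)^10 = 40%, 65% and 89% for d = 5%, 10% and 20%. The rules disagree on *better than 50%* when the nested count is 9 or more and the present count is 8 or fewer.

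| pN | d = 5% | d = 10% | d = 20% |
|---|---|---|---|
| 80% | 13% | 23% | 33% |
| 70% | 6% | 10% | 14% |
| 60% | 2.3% | 3.6% | 4.5% |
| 50% (protocol's expectation) | 0.6% | 0.9% | 1.1% |

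At pN = 50%, disagreement on *worse than 50%* (nested count 2 or more, present count 1 or fewer) is 1.3%, 3.6% and 13.9%.

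**The case against.** **The text does not settle every case.** *Abnormal* creatinine is undefined. CR item 1a refers to the patient's own baseline, so *abnormal* could mean changed from the usual level. The chronically stable patient would then have no abnormal creatinine to improve and would be a PR. Likewise, if the usual level were 1.4 (illustrative) and 50% meant half the excess over it, 2.0 to 1.7 recovers 0.3/0.6 = 50% and passes. This stands: a reader might infer that such patients can never be PR, and that is too strong. But the protocol nowhere states the softer reading, and the literal one excludes them.

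**No CR patient is lost.** Responders are CR plus PR, so any loss falls only on patients who miss CR. This also stands. A demanding creatinine rule for PR is a legitimate choice, and part of the 0.4 versus 0.6 contrast is the ordinary effect of a cut-off. Counting a 6.7% eGFR change as deterioration is the harshest reading.

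**The size is assumed.** No document gives d. With total response 50% and CR 20%, PR is 30%, so d = 20% means that 20/30, two-thirds, of partial responders fail on this rule, which is extreme. One patient moving an arm by 10 points is a consequence of 10 per arm under any definition. These limits stand, which is why the figures are a range.

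**A tempting inference about bias.** A reader might conclude that the present rule biases total response downwards against the 50%. The documents do not support that: the definitions behind the 50% are in Table 1, which is not shown, and one described comparator does not fix the rest.

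**Conclusion.** The point holds on a literal reading: CR and PR are not nested on kidney function, and non-CR patients with a raised creatinine that is stable or improved by less than half are counted as non-responders. The effect is confined to the secondary total-response comparison with 50% and the time-to-partial-remission analysis. A reader might infer that the primary endpoint or the comparison between arms is compromised. Neither follows: CR against 20% does not use the PR rule, and the same rule applies in both arms.

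The direction and size of any bias are unknown. At the cut-offs one patient decides the result. Across the assumed range, disagreement on *better than 50%* runs from about 1% at the protocol's expected total response to 33% at a nested response of 80% with 20% discordance. This is a cheap improvement to a secondary endpoint, not a flaw in the trial's main result.

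**What to change.** For endpoint analysis only:

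1. Keep the present PR rule as the main version. Before analysis, state what counts as *abnormal* creatinine, whether 50% refers to the absolute value or an excess, which baseline applies (Study Drug Discontinuation names visit 0), and what tolerance applies to *deterioration*.
2. Add one pre-specified sensitivity analysis of total response. A responder is any CR, or a patient with at least a 50% fall in UPCR from the study-entry value (the one required to exceed 1) and eGFR no more than 10% below baseline or improved. Counting any CR makes the levels nested by construction. The definition needs this because a UPCR at visit 0 may be lower than at entry, for instance after an ACE inhibitor or ARB is started during screening: 0.9 to 0.48 meets the CR limit but is a fall of only 0.42/0.9 = 47%.
3. Report both versions per arm with exact 95% CIs against 50%. If they disagree, say that the conclusion depends on the PR rule. Do not assume that the added total can never be lower: with a deterioration tolerance looser than 10%, a present PR could breach the added eGFR limit.
4. In the time-to-event analysis, count reaching CR as at least partial remission.

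The cost is wording in the secondary outcome and the analysis plan, plus one analysis of data already collected for CR. The downside is two versions to report and possibly a more cautious conclusion.

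Separately, Treatment Description offers continued ACTHar to partial responders, while Dosage and Administration of Acthar offers it to patients without CR at week 12. The sponsor must reconcile these sections; the endpoint wording should not alter that treatment rule.
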